**Table 4** **Intervals between study visits**

Interval	Optimal timing	Allowed interval
Screening Visit→ Visit 1	≤7 days	-7 - 1 days*
Visit 1 → Visit 2	8 days	7 - 10 days
Visit 1 → Visit 3	31 days	30 - 45 days
Visit 1 → Phone Contact 1	181 days	165 - 195 days
Visit 4 → Visit 5	≤7 days	-7 to 1 days*
Visit 1 → Visit 5	365 days	365 - 548 days**
Visit 5 → Phone Contact 2	8 days	7 - 10 days
Visit 5 → Visit 6	31 days	30 - 45 days
Visit 5 → Phone Contact 3	181 days	165 - 195 days

\*From 7 days prior to vaccination up to and including the day of vaccination.

\*\* For a 6-month period ≥12 to <18 months post 1st vaccination

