
 
To evaluate the humoral immune response to 2 dose levels (60 and 120 µg) of RSVPreF3 when given alone and co-administered with dTpa, at Screening, Day 8 and Day 31 post 1st dose vaccination
 
	
 
RSV A neutralizing antibody titers at Screening, Day 8 and Day 31 in all groups
 
RSV IgG antibody concentrations at Screening, Day 8 and Day 31.
 

Secondary (US and ex-US data to be considered pooled, then separately)	
Safety	Safety

 
To evaluate the safety and reactogenicity of 2 dose levels (60 and 120 µg) of RSVPreF3 when given alone or co-administered with dTpa from 1st dose vaccination up to Day 31 by formulation.
 
	
 
Occurrence of any AEs from Vaccination to Day 31, for all subjects: 
 
Occurrence of each solicited local AE at the site of injection in both limbs from Vaccination to Day 8
 
Occurrence of solicited general AEs from Vaccination to Day 8
 
Occurrence of any unsolicited AEs from Vaccination to Day 31
 
Occurrence of Serious Adverse Events (SAEs) from Vaccination to Day 31.
 
 
 

**CONFIDENTIAL**209141 (RSV MAT-011)  
Protocol Amendment 6 Final

Objectives	Endpoints

 
To evaluate the safety of 2 dose levels (60 and 120 µg) of RSVPreF3 when given alone and co-administered with dTpa compared to dTpa-Placebo groups from 1st dose vaccination up to Day 181.
 
	
 
Occurrence of SAEs from Vaccination up to Day 181.
 

 
To evaluate the safety of 2 dose levels (60 and 120 µg) of RSVPreF3 when given alone and co-administered from Vaccination up to Day 181 by formulation.
 
	
 
Occurrence of SAEs from Vaccination up to Day 181.
 

 
To evaluate the safety of RSVPreF3 (pooled for all groups receiving RSVPreF3) for the 1st dose vaccination.
 
	
 
Occurrence of SAEs from Vaccination up to Day 181.
 

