
 
To evaluate the safety of 2nd dose of RSVPreF3 given from 12 to up to 18 months post 1st dose vaccination up to Day 181 post 2nd dose vaccination.
 
	
 
Occurrence of SAEs from 2nd dose vaccination up to Day 181 post-2nd dose vaccination.
 

Immunogenicity	Immunogenicity

 
To evaluate the humoral immune response and persistence to 2 dose levels (60 and 120 µg) of RSVPreF3 when given alone and co-administered with dTpa at Screening, Day 8, and Day 31 post 1st dose vaccination, and at 12 to 18 months by formulation.
 
	
 
RSV A neutralizing antibody titers at Screening, Day 8, Day 31, and a single timepoint between 12 to 18 months post 1st vaccination.
 
RSV IgG antibody concentrations at Screening, Day 8, Day 31, and a single timepoint between 12 to 18 months post 1st vaccination.
 

 
To evaluate the humoral immune response to the pertussis component of the dTpa vaccine when given alone and co-administered with 2 dose levels (60 and 120 µg) of RSVPreF3 at Screening and Day 31 post 1st dose vaccination by formulation.
 
	
 
Antibody concentrations against pertussis toxoid (anti-PT), filamentous hemagglutinin (anti-FHA), and pertactin (anti-PRN) concentrations at Screening and Day 31.
 

 
To evaluate the humoral immune response to the diphtheria (D) component of dTpa vaccine when given alone and co-administered with 2 dose levels (60 and 120 µg) of RSVPreF3 at Screening and Day 31 post 1st dose vaccination by formulation.
 
	
 
Anti-D concentrations at Screening and Day 31.
 

 
To evaluate the humoral immune response to the tetanus (T) component of dTpa vaccine when given alone and co-administered with 2 dose levels (60 and 120 µg) of RSVPreF3 at Screening and Day 31 post 1st dose vaccination by formulation.
 
	
 
Anti-T concentrations at Screening and Day 31.
 

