**CONFIDENTIAL**

209141 (RSV MAT-011)  
Protocol Amendment 6 Final

\*All subject groups will be given RSV 120mcg and subjects will be followed in an unblinded open label manner

\*\* Hematological and biochemical laboratory testing at Visit 4 (D -7 up to and including 2nd dose vaccination) at the investigator's discretion

\*\*\* There will be no follow-up between C1 and V4. New medical history and relevant new safety events during this period will be recorded at visit 4 for subjects who agree to the study extension and sign the informed consent addendum.

**CONFIDENTIAL**209141 (RSV MAT-011)  
Protocol Amendment 6 Final

The study will be conducted with 2 formulations of dTpa, dTpa\_300 (in the US) and dTpa\_500 (ex-US).

Approximately 500 eligible subjects (250 in the US and 250 ex-US) will be enrolled. Of these, approximately 250 subjects will be randomized to 5 US study groups in a 1:1:1:1:1 ratio using SBIR, and the remaining approximately 250 will be randomized to 5 ex-US study groups in a 1:1:1:1:1 ratio using SBIR. The randomization algorithm will use a minimization procedure by treating study formulation (US and ex-US) as a stratification factor, and age at the time of vaccination (18-32 or 33-45 years of age) and center as minimization factors.

Protocol waivers or exemptions are not allowed unless necessary for the management of immediate safety concerns. Therefore, adherence to the study design requirements, including those specified in the schedule of activities (Section 2), are essential and required for study conduct.

- Type of study: self-contained
- Experimental design:
  - Primary Vaccination: multi-centric study, multi-country Phase II, observer-blind, randomized, with 5 parallel groups in each formulation (US, ex-US).
- Study Extension: multi-centric study, multi-country Phase II, open unblinded, with all 5 parallel groups in each formulation (US, ex-US) receiving the experimental RSV maternal (120 $\mu$ g) vaccine.
- Duration of the study: The primary study will be approximately 6 months for each enrolled subject and from 18 up to 24 months for subjects that agree to participate in the study extension.
  - Primary Vaccination
    - Epoch 001: Screening
    - Epoch 002: Primary vaccination starting at Visit 1 (Day 1) and ending just before the Visit 3 (Day 31)
    - Epoch 003: Follow-up after Visit 3 (Day 31) to Phone Contact 1 on (Day 181)

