### **8.5.1. Safety definitions**

Please refer to Section [12.5](#) for safety definitions.

**CONFIDENTIAL**209141 (RSV MAT-011)  
Protocol Amendment 6 Final**8.5.2. Time period and frequency for collecting AE and serious adverse event (SAE) information**

An overview of the protocol-required reporting periods for AEs, SAEs, and pregnancies is given in [Table 14](#). Refer to the Section [12.5.7.1](#) for details on the time period for recording safety information.

CONFIDENTIAL

209141 (RSV MAT-011)  
Protocol Amendment 6 Final**Table 14 Reporting periods for collecting safety information**

Event	Pre-V1*	V1	V2	V3	C1	C1 to V4**	V4	V5*		C2		V6	C3	
		D1	D7	D8	D30	D31	D181		D - 7 up to 2 nd vaccination	2 nd vaccination From 12 up to 18 months post 1 st vaccination	D7 post second 2 nd vaccination	D8 post second 2 nd vaccination	D30 post second 2 nd vaccination	D31 post 2 nd vaccination
Solicited local and general AEs														
Unsolicited AEs														
AEs leading to withdrawal from the study														
SAEs**														
SAEs related to study participation or concurrent GSK medication/vaccine														
Pregnancies***														

\* i.e. consent obtained. Pre-V: pre-vaccination; V: vaccination; Post-V: post-vaccination; D: Day, M: Month

\*\* There will be no follow-up between C1 and V4. New medical history and relevant new safety events during this period will be recorded at visit 4 for subjects who agree to the study extension and sign the informed consent addendum. In addition, SAE related to vaccination are reported during the period C1-V4 will be reported to the Investigator at the time of awareness.

\*\*\*Pregnancies that occurred during the C1-V4 period will be reported as medical history

**CONFIDENTIAL**209141 (RSV MAT-011)  
Protocol Amendment 6 Final

All SAEs will be recorded and reported via Expedited AE Reporting Form to the sponsor or designee immediately and under no circumstance should this exceed 24 hours after the investigator became aware of it, as indicated in Section 12.5. The investigator will submit any updated SAE data to the sponsor within 24 hours of it being available.

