## **9. DISCONTINUATION CRITERIA**

### **9.1. Discontinuation from the study**

Subjects will complete the study at day 181 with a phone contact. For the subjects that enroll in the study extension, the conclusion of the study will be on Day 181 following the second immunization as described in the protocol.

From an analysis perspective, a 'withdrawal' from the study refers to any subject was not available for the concluding contact foreseen in the protocol.

All data and samples collected until the date of withdrawal/last contact of the subject will be used for the analysis.

A subject is considered a 'withdrawal' from the study when no study procedure has occurred, no follow-up has been performed and no further information has been collected for this subject from the date of withdrawal/last contact.

Investigators will make 3 attempts followed by a certified letter to contact those subjects who do not return for scheduled visits or follow-up.

**CONFIDENTIAL**209141 (RSV MAT-011)  
Protocol Amendment 6 Final

Primary reason for study withdrawal will be documented in the eCRF. The investigator will document whether the decision to withdraw a subject from the study was made by the subject himself/herself, or by the investigator, as well as which of the following possible reasons was responsible for withdrawal:

- Adverse events requiring expedited reporting
- Unsolicited non-serious adverse event
- Solicited adverse event
- Protocol deviation
- Withdrawal by subject, not due to an adverse event\*
- Migrated/Moved from the study area
- Lost to follow-up
- Sponsor study termination
- Other (specify)

\*In case a subject is withdrawn from the study because she has withdrawn consent, the investigator will document the reason for withdrawal of consent, if specified by the subject in the eCRF.

Subjects who are withdrawn from the study because of SAEs/AEs must be clearly distinguished from subjects who are withdrawn for other reasons. Investigators will follow subjects who are withdrawn from the study as result of a SAE/AE until resolution of the event (see Section 12.5.10).

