Secondary	
(US and ex-US data to be considered pooled, then separately)
 
For each group with 1st dose vaccination of RSVPreF3 (two dose level) when given alone or co-administered with dTpa; the following points will be analysed for 1st and 2nd dose vaccination.
 
The percentage of subjects with at least one local AE with at least one general AE and with any ("solicited or unsolicited") AE during the 7-day or 30 -day follow-up as well any SAE up period to 180 days post 1st and 2nd vaccination time points will be tabulated with exact 95% CI by study group. The same computations will be done for Grade 3 AEs, for any AEs considered related to vaccination, for Grade 3 AEs considered related to vaccination and for AEs resulting in medically attended visits and AEs leading to withdrawal from study.
 
The percentage of subjects with at least one report of SAE classified by the MedDRA SOC and Preferred Terms and reported during the 30-day or 180-day follow-up period will be tabulated with exact 95% CI for each formulation (US and ex-US).
 
The percentage of subjects reporting each individual solicited local AE on left or Right arms (any grade, Grade 3 and those resulting in a medically attended visit) and solicited general AE (any grade, Grade 3, any related, Grade 3 related and those resulting in a medically attended visit) during the 7-day follow-up period (i.e. on the day of vaccination and 6 subsequent days) will be tabulated based on maximum intensity for each group for each formulation (US and ex-US).
 
For fever, the number and percentage of subjects reporting fever by half degree (°C) cumulative increments during the 7-day follow-up period will be tabulated for each group for each formulation (US and ex-US). Similar tabulations will be performed for any fever with a causal relationship to vaccination, Grade 3 or above ($> 39.0^{\circ}\text{C}/102.2^{\circ}\text{F}$) causally related fever, and fever resulting in a medically attended visit. In addition, the prevalence of any and Grade 3 fever will be presented graphically over time after each vaccination.
 
For each formulation (US and ex-US), the percentage of subjects with any unsolicited AEs during the 30-day follow-up period (i.e. on the day of vaccination and 29 subsequent days) with its exact 95% CI will be tabulated by group and by Medical Dictionary for Regulatory Activities (MedDRA) SOC and preferred term. Similar tabulation will be done for Grade 3 unsolicited AEs, for any causally related unsolicited AEs, for Grade 3 causally related unsolicited AEs and for unsolicited AEs resulting in a medically attended visit. The verbatim term of unsolicited AEs will

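### The closing safety calls C1 and C3 may be made up to 16 days before the Day 181 SAE endpoint closes, and the SAP has no rule for women called early; the effect is small and matters mainly for C3.

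*Protocol*

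**What the plan says.** **Call windows.** Protocol Table 4 (Section 2) gives "Visit 1 → Phone Contact 1 181 days 165 - 195 days" for the call after dose 1 (C1) and "Visit 5 → Phone Contact 3 181 days 165 - 195 days" for the call after dose 2 (C3). Table 10 (Section 8.1) leaves both windows unchanged under special circumstances.

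**Endpoints.** Table 5 (Section 4) uses "Occurrence of SAEs from Vaccination up to Day 181" as the endpoint of three dose-1 secondary safety objectives. For dose 2 it uses "Occurrence of SAEs from 2 nd dose vaccination up to Day 181 post-2 nd dose vaccination".

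**What the call closes.** The Schedule of Activities (Table 3) marks C1 as the conclusion of the primary study and C3 as the conclusion of the extension. Section 9.1 says "Subjects will complete the study at day 181 with a phone contact". The Table 14 footnote (Section 8.5.2) adds "There will be no follow-up between C1 and V4". Under Section 8.5.5 investigators need not look for SAEs in former participants, and must notify a post-study SAE they learn of only if they consider it related.

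**What remains after C1.** A footnote to Figure 1 (Section 5.2) says that "relevant new safety events during this period will be recorded at visit 4 for subjects who agree to the study extension". Table 3 marks SAE recording in the eCRF at Visit 4. Section 8.3.2 sends significant medical conditions from the C1 to Visit 4 period to medical history. The Table 14 footnote has vaccination-related SAEs in that period reported on awareness.

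**Analysis.** SAP Section 5.3.1 words the secondary safety table like this: "as well any SAE up period to 180 days post 1st and 2nd vaccination time points will be tabulated with exact 95% CI by study", that is, for each group. The Exposed Set (SAP 4.1.1) requires at least one dose and sets no condition on length of follow-up.

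**The concern.** The schedule lets the last SAE question be asked before the endpoint period has ended. A woman called on Day 165 who is hospitalised on Day 172 for a reason judged unrelated has an event inside the endpoint, but nobody is scheduled to ask her about it. A late call cannot make up for an early one, because events after Day 181 lie outside the endpoint.

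The other post-vaccination windows in Table 4 do not behave this way. Visit 2 and Phone Contact 2 open at 7 days against a target of 8, and Visits 3 and 6 open at 30 days against a target of 31. Only C1 and C3 open well before their target.

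At stake are the absolute SAE percentages to Day 181, which are the quantity these secondary objectives report.

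**Working it through.** **1. The plan's own precision figures** (Protocol Section 10.1.2, 400 RSVPreF3 recipients)

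- Probability of at least one event at a true risk of 1%: 1 − 0.99^400 = 98.2% (stated 98%).
- Exact two-sided 95% upper limit with no events: 1 − 0.025^(1/400) = 0.92% (stated 0.9%).

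Both reproduce. The documents give no figure for the call-window gap.

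**2. Largest gap**

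- Day 181 endpoint, call on Day 165: 181 − 165 = 16 days; 16/181 = 8.8%.
- SAP 180-day horizon: 180 − 165 = 15 days; 15/180 = 8.3%.
- If 165 days means elapsed days, the call falls on Day 166: 181 − 166 = 15 days.

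The two horizons are not obviously the same. SAP 5.3.1 defines its 30-day period as the vaccination day plus 29 days. By analogy, 180 days would end on Day 180.

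**3. Average gap, assuming calls spread evenly over Days 165 to 195**

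- Call days before Day 181: 16 of 31 (52%).
- Mean days lost over all women: (16 + 15 + … + 1)/31 = 136/31 = 4.4 days; 4.4/181 = 2.4%.

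**4. Effect on the SAE estimate**, assuming a constant hazard and that nothing after the call is captured. Observed risk = 1 − (1 − p)^(T/181), where T is the last day observed.

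| Quantity (400 women, true risk 1% assumed) | Full follow-up | Even spread (T = 176.6) | Every call on Day 165 |
|---|---|---|---|
| Observed risk | 1.00% | 0.976% | 0.912% |
| Expected cases missed | 0 | 0.10 | 0.35 |
| Probability of at least one case | 98.2% | 98.0% | 97.4% |

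With every call on Day 165, the zero-event limit becomes 1 − (1 − 0.00918)^(181/165) = 1.01% instead of 0.92%. Expected missed cases among 400 at other assumed risks are 0.18 (0.5%), 0.70 (2%) and 1.7 (5%). For C3, if all 500 women entered the extension (an upper limit), the figure at 1% is 0.44.

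**5. Who is exposed to the gap**

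- *After C3:* everyone called early. No later visit exists, so an SAE in the remaining days is captured only if the woman reports it or the investigator learns of a related one.
- *After C1, no extension:* unrelated SAEs. Related ones are reportable on awareness.
- *After C1, extension:* Visit 4 asks about the period, roughly 6 to 12 months later and after treatment has been disclosed (Section 7.3). Table 3 and the Figure 1 footnote point to SAE and safety-event recording, whereas Section 8.3.2 points to medical history. Neither says whether the event enters the Day 181 table. The second analysis is triggered by completion of C1 (Protocol 10.4, SAP 7.1.1), so it need not wait for Visit 4.

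**The case against.** The case for leaving the plan alone is substantial.

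- *The events are not simply lost.* A reader might infer that the days after an early call are never observed. The documents do not support that. Visit 4 covers extension women, and related SAEs are reported on awareness. Section 12.5.7 tells women to contact the investigator at once about anything they perceive as serious. This stands for C1 and is only a partial answer for C3.
- *The reporting duty may run to Day 181 regardless of the call.* Section 8.5.5 defines a post-study event by Table 14, where the C1 column is headed D181. The shading of that table is not legible in the text available. If it runs to Day 181, an SAE on Day 170 is still reportable once known. That is fair, but a duty to report is not a contact that asks the question.
- *The SAP nowhere says that every woman was followed to Day 181.* One might read that into the Exposed Set denominator, but it is an inference: a crude percentage of exposed women also includes withdrawals. What stands is that no rule addresses early calls.
- *The effect is very small.* The target is 181 days and nothing suggests that sites call early. Even the worst case costs about a third of one expected case in 400 at 1% risk. The study is descriptive (Section 10.1.1). This stands, and it limits the weight of the point.
- *C1 can hardly be changed now.* Extension women must have completed the primary study (Section 6.3). This stands, so a prospective change is mainly for C3.

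**Conclusion.** The point holds in limited form. A stated rule allows a compliant closing call up to 16 days before the SAE endpoint closes (15 on the SAP wording), active follow-up ends there, and the SAP does not say how women called early are handled. The loss is at most 8.8% of the observation time. It averages about 2.4% if calls are spread evenly, which is an assumption; the case counts further assume a constant hazard and no capture after the call. Absolute SAE percentages are lowered slightly.

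Two further inferences are not supported. The window is identical in all groups, so it does not bias the comparison with dTpa plus placebo. Nor are pregnancy rates biased: pregnancy is not an endpoint in Table 5, the current SAP plans no pregnancy table, and pregnancies between C1 and Visit 4 are recorded as medical history.

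This is a cheap improvement, not a threat to the study's conclusions. It matters most for C3, which has no later visit.

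**What to change.** 1. In Tables 4 and 10, open the Visit 5 to Phone Contact 3 window no earlier than Day 181, and likewise the Visit 1 to Phone Contact 1 window where that call is still to come. A window of 181 to 211 keeps the present width (195 − 165 = 211 − 181 = 30 days).
2. For women already called before Day 181, state in SAP 5.3.1 that SAEs with onset up to Day 181 count in the Day 181 table whenever they are learned of, including at Visit 4. Align Protocol Section 8.3.2 with Table 3 and the Figure 1 footnote, so that such an event is not left only in medical history.
3. Report, by group and dose, the number of women called before Day 181 and their follow-up duration.
4. Reconcile the SAP's 180 days with the protocol's Day 181.

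Cost: two cells in each of two tables, a few sentences in the SAP and one descriptive summary. No procedure or visit is added. The downside is a slightly later closing call: with 181 to 211 the latest permitted date moves by 16 days (211 − 195), and the last subject's last contact could move with it.

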### 3. INTRODUCTION

#### 3.1. Study rationale

GSK is developing an investigational RSV maternal vaccine (RSVPreF3) against RSV disease in infants through maternal immunization. In the RSV maternal program to date, a Phase 1/2 study (study RSV MAT-001; NCT 03674177) is ongoing in healthy non-pregnant women 18-45 years of age (YOA) to determine the safety and immunogenicity of 3 dose levels of RSVPreF3 (30, 60 and 120 µg) compared to placebo. Preliminary safety information is available in the investigator brochure.

In many countries, the use of acellular pertussis vaccination is recommended for women during pregnancy to protect young infants against pertussis before they can benefit from the infant vaccination series [Mazzilli, 2018]. *Boostrix*, a vaccine against diphtheria, tetanus and acellular pertussis is administered in the third trimester of pregnancy in many countries. Since RSVPreF3 is intended for administration in the third trimester of pregnancy, it will be important to evaluate any potential interference of co-administration with *Boostrix*.

This study (RSV MAT-011), in healthy non-pregnant women, will be the first to evaluate co-administration of RSVPreF3 with *Boostrix* (dTpa). Selection of the 60 and 120µg RSVPreF3 doses was based on preliminary results of the ongoing (RSV MAT 001) Phase 1/2 study.

Two formulations of dTpa vaccine, one containing 300 micrograms and the other containing 500 micrograms of aluminum are licensed in the US and outside the US (ex-US), respectively. As such, the *Boostrix* (US formulation) (dTpa\_300) will be administered to subjects in centers located in the US, while the *Boostrix* (ex-US formulation) (dTpa\_500) will be administered to subjects in centers ex-US. In previous studies both, *Boostrix* formulations have had a similar immunogenicity and safety profiles. Therefore, any potential differences in immune response to *Boostrix* in this study

**CONFIDENTIAL**209141 (RSV MAT-011)  
Protocol Amendment 6 Final

may be the result of population differences or immune response in the setting of RSVPreF3 co-administration [[Theeten](#), 2005].

This will be a Phase II study to evaluate safety and reactogenicity of co-administration of RSVPreF3 and dTpa\_300 or dTpa\_500 in non-pregnant women 18-45 YOA. Additionally, this study will evaluate whether co-administration of dTpa affects the magnitude of the immune response to RSVPreF3 and whether RSVPreF3 affects the magnitude of the immune response to dTpa.

Finally, a second dose vaccination of RSVPreF3 (120 µg) will be administered to the consenting subjects from 12 to 18 months following initial vaccination to evaluate the immunogenicity and safety profile of RSVPreF3. This extension of the study will recruit the same non-pregnant women as a proxy for women who may require additional dosing in successive pregnancies.

